#### **Drugs**

MDMA (1.5mg/kg) will be placed in opaque size 00 capsules with lactose (USP) filler. Placebo capsules will contain only lactose. These doses have previously been safely administered to healthy human participants (Mayo et al., 2013, 2014, Kirkpatrick et al. 2011). MDMA will be obtained in powder form from Organix Inc, MA under Investigational New Drug (IND) license # 76,536.

Capsule contents will be prepared and used within eight weeks of encapsulation. We have used similar doses of MDMA in previous studies without adverse reactions (Wardle and de Wit, 2014, Bedi et al, 2009). Participants will be closely monitored during sessions and a physician will be on call during and after sessions.

**Measures:** Measures will include measures of emotional traits, which are taken one time at orientation, and subjective measures of mood state, drug effects and responses to stimuli, fMRI of brain activity, and physiological assessment of blood pressure, heart rate, and salivary oxytocin.

#### Measures Taken During Screening Only

1. Autism Spectrum Quotient questionnaire (Baron-Cohen et al. 2001) is a 50-item survey designed to assess five dimensions of autism spectrum traits. Scores range from 0-50, with a score of 32+ likely to indicate clinically significant symptoms. We will recruit individuals with a range of scores on the questionnaire, with 12-14 each from the 0-10 range, 10-20 range, and 20-32 range.
2. Social Anxiety Questionnaire (Caballo et al, 2012). This standardized questionnaire provides a quantitative measure of social anxiety in a range of social conditions.

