Our laboratory has conducted a series of behavioral studies with the psychostimulant drug ±3,4-methylenedioxymethamphetamine (MDMA), a drug that rapidly increases both oxytocinergic and serotonergic signaling. MDMA increases synaptic levels of serotonin, and increases plasma levels of oxytocin to a greater extent than intranasal administration of oxytocin itself (Kirkpatrick et al. 2014). Behaviorally, MDMA facilitates social behaviors, including those implicated in ASD, in both rodent models and healthy human volunteers (Kamilar-Britt and Bedi 2016), suggesting that it may have potential in the treatment of autism. Indeed, one recent study reported that MDMA reduces social anxiety in individuals with autistic traits (Danforth et al.

2018). To date, however, no controlled laboratory studies have investigated the neurobiological actions of MDMA in individuals with autistic traits, and little is known about how the drug affects behavioral indices of the social communication deficits, such as affective touch. We propose to address this gap in knowledge by testing the acute effects of MDMA, compared to placebo, on subjective, neural, and hormonal responses to affective touch in individuals with mild autistic-like traits.

**Specific Aim 1: To determine the effects of MDMA on subjective responses to affective touch in individuals with a range of mild autistic-like traits**

Our preliminary data suggest that MDMA enhances pleasantness ratings of affective touch in healthy adult volunteers (Bershad et al. 2019). Here we will extend this finding to individuals with symptoms of ASD. Adult volunteers with a range of mild autistic-like traits (N=45) as measured by the Autism Spectrum Quotient (ASQ) will attend two laboratory sessions during which they will be given placebo or 1.5mg/kg MDMA (oral). At the expected time of peak drug effect, they will complete behavioral tasks assessing responses to affective touch. We hypothesize that individuals with higher ASQ scores will rate the pleasantness of affective touch lower than those with low ASQ scores, and that MDMA will ameliorate this effect, increasing pleasantness ratings to levels similar to those of the low ASQ group without MDMA.

**Specific Aim 2: To determine the effects of MDMA on neural responses to affective touch in individuals with a range of autistic traits.**

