**Methods:**

**Design:** The study will use a 2-session within-subjects double blind design in which participants will receive MDMA or placebo in randomized order. Participants will vary in scores on the Autism Spectrum Quotient (ASQ). On each of two 4.5-hour sessions participants will first report to the Human Behavioral Pharmacology Laboratory suite for drug administration, and then they will be escorted to the MRI Research Center (MRIRC) for the fMRI scan. Subjective ratings will be obtained at regular intervals throughout the session and performance on the tasks, as well as neural measures of activation, will be obtained during the scans.

**Subjects:** 45 healthy volunteers (22 male, 23 female; age range 21-40 years) will participate in the experiment. Sample size was determined with a power analysis on preliminary data showing

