MDMA increases pleasantness ratings of touch ( $d=0.44$ ). Recruiting 45 subjects will provide greater than 80% power to detect an effect. Based on our previous rates of participants completing all four sessions after enrolling in the study, to recruit 45 subjects, we will need to consent 60 participants. Subjects will complete the Autism Spectrum Quotient (ASQ), and we will recruit individuals with a range of scores on the questionnaire, with 15 each from the 0-10 range, 10-20 range, and 20-32 range. Subjects with clinically significant ASD, as determined by our screening interviewers and the participants' responses to questions during the psychiatric screening interview will not be included in the study and will be referred for treatment. In particular, any participants who have difficulty understanding or complying with the study requirements will be ineligible. Subjects will also complete the Social Anxiety Questionnaire (Caballo et al, 2012). All participants will be recruited without regard to race, religion or ethnicity through posters, advertisements and word-of-mouth referrals. Candidates will be screened in accordance with our general screening protocol, approved by the IRB under Protocol #13681B, which includes a physical, EKG, psychiatric screening interview and detailed drug use history questionnaire. We will enroll individuals who report having used ecstasy at least 4 times but not more than 40 times, with no adverse responses. Because MDMA will be administered as part of the study, the following populations are excluded for safety reasons: Individuals with a BMI  $<19$  or  $>30$ , or weighing under 130 lbs, as this alters dosing requirements; Individuals with high blood pressure, abnormal EKG, any medical condition requiring regular medication, or any other medical contraindication to MDMA administration as determined by our study physician; Individuals with a current (within the last year) DSM-IV Axis I diagnosis, excluding non-treatment seeking drug abuse; Individuals with a history of dependence on stimulant drugs; Women who are pregnant. Smokers smoking more than 25 cigarettes per week will also be excluded, to avoid confounding the effects of nicotine withdrawal with the effects of the study drugs/procedures, as participants will not be allowed to smoke during the sessions. The self-report questionnaires we use require fluency in English, and have not been translated and validated in other languages, thus individuals with less than a high-school education or those not fluent in English will be excluded.

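### The screening-measures section recruits 12-14 per ASQ band (36-42 in all), which conflicts with 15 per band and N=45 elsewhere in the protocol

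*Combined protocol and SAP*

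**What the plan says.** Two current sections of the combined protocol and SAP give recruitment numbers for the same three ASQ bands.

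- **Measures Taken During Screening Only, item 1 (ASQ):** "with 12-14 each from the 0-10 range, 10-20 range, and 20-32 range".
- **Methods, Subjects:** "with 15 each from the 0-10 range, 10-20 range, and 20-32 range".

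The total of 45 appears in three statements:

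- **Specific Aim 1:** "Adult volunteers with a range of mild autistic-like traits (N=45" and so on.
- **Methods, Subjects, opening sentence:** "45 healthy volunteers (22 male, 23 female; age range 21-40 years".
- **Methods, Subjects, sample size:** "Recruiting 45 subjects will provide greater than 80% power to detect an effect", followed by the consent target, "to recruit 45 subjects, we will need to consent 60 participants".

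The Data Analysis section uses the same three bands (low, medium, high) as the between-subjects factor.

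**The concern.** The two band quotas cannot both be followed. The quota fixes the total sample size and also the size of each group in the planned ANOVA. Anyone who fills the bands from the ASQ item would close recruitment below the N on which the power statement rests. That item is where the questionnaire and its score ranges are described, so it is a plausible place to look the quota up.

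**Working it through.** **1. Totals from the stated quotas.**

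| Source | Per band | Bands | Total | Difference from 45 |
|---|---|---|---|---|
| Methods, Subjects | 15 | 3 | 45 | 0 |
| ASQ item, upper end | 14 | 3 | 42 | 3 (6.7%) |
| ASQ item, lower end | 12 | 3 | 36 | 9 (20%) |

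The sex split agrees with the larger total: 22 + 23 = 45.

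**2. Can the two be reconciled?** The shared boundaries at scores 10 and 20 do not help. Counting one person in two bands would lower the number of distinct participants, not raise it to 45. The ASQ item does not say that its numbers refer to completers or to participants with usable scans. Nothing in either section is marked as superseded.

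**3. The plan's own power figure.** Inputs from the Subjects paragraph: d = 0.44 and N = 45. The test, alpha, sidedness and type of d are not given. I assume a paired t-test, two-sided alpha 0.05, and d as the mean difference divided by the SD of the differences. Then the noncentrality is d × √N with N − 1 degrees of freedom, and power is the probability that the noncentral t falls beyond the critical value.

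- N = 45: 0.44 × √45 = 2.952, critical t(44) = 2.015, power **82.3%**. This agrees with the stated figure of more than 80%.

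**4. The same calculation at the ASQ item's totals.**

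- N = 42: 0.44 × √42 = 2.852, critical t(41) = 2.020, power **79.5%**.
- N = 36: 0.44 × √36 = 2.640, critical t(35) = 2.030, power **72.8%**.
- The smallest N with at least 80% is 43 (80.5%).

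**5. Sensitivity to what is not stated.** If d is on the raw SD, the paired effect size is d / √(2(1 − r)), where r is the within-person correlation. At r = 0.6 this is 0.44 / √0.8 = 0.492. The value of r is not in the documents, so a range is shown.

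| Reading (alpha 0.05) | N = 36 | N = 42 | N = 45 |
|---|---|---|---|
| Paired t, two-sided, paired d | 72.8% | 79.5% | 82.3% |
| Normal approximation, two-sided, paired d | 75.2% | 81.4% | 83.9% |
| Paired t, one-sided, paired d | 82.7% | 87.7% | 89.6% |
| Paired t, two-sided, d on raw SD, r = 0.3 | 58.3% | 65.3% | 68.4% |
| Same, r = 0.5 | 72.8% | 79.5% | 82.3% |
| Same, r = 0.6 | 81.9% | 87.5% | 89.7% |
| Same, r = 0.7 | 91.2% | 94.9% | 96.1% |

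The r = 0.3 row does not give the stated 80% even at N = 45. On the raw-SD reading, the power statement needs r of about 0.47 or more. The rows show how far the answer moves with the assumption. They are not equally likely alternatives to be counted.

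**The case against.** The strongest reply is that the Subjects paragraph governs sample size, and it is clear: 45 participants, 15 per band, 60 to consent. Specific Aim 1 agrees. The ASQ item describes a questionnaire, and that staff would take quotas from it is conjecture. This stands and keeps the severity low, but it does not remove the conflict, because the ASQ item is itself worded as a recruitment commitment.

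A second reply is that 12-14 might be the number per band expected after losses. The shared use of the word recruit does not settle this by itself. The Subjects paragraph bases its consent target on past rates of session completion, so there the word comes close to meaning completers. The Data Analysis section also excludes participants for head movement, a loss that the consent target does not mention. What defeats the reply is simpler: the ASQ item does not say that its figure is net of anything.

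A reader might go further and infer that the study as written is underpowered. The documents do not support that. The stated power is for N = 45, and it reproduces under the paired reading above. At 36 to 42, whether power drops below 80% depends on a test, sidedness and type of d that the protocol does not give. At 42 the shortfall under the two-sided paired t-test is only half a percentage point, and under the normal approximation there is none.

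**Conclusion.** The inconsistency is real and needs no assumption: 36 to 42 under one section, 45 under the others, a gap of 3 to 9 participants. Its effect on power is conditional. With a two-sided paired t-test at 0.05 and d = 0.44 as the paired effect size, power would fall from 82.3% to between 72.8% and 79.5%. With a one-sided test, or with d on the raw SD and r of 0.6 or more, it would stay above 80% even at 36. A loss of power is therefore possible but not established. It should be corrected, at low severity, because the Subjects paragraph already carries the intended total and quota.

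**What to change.** In Measures Taken During Screening Only, item 1, replace the per-band figure of 12-14 with 15, so that the clause matches the Subjects paragraph: "with 15 each from the 0-10 range, 10-20 range, and 20-32 range". This is the only single edit that brings all the sections into agreement. Keeping 12-14 would mean rewriting the total N, the sex split, the consent target and the power statement.

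The cost is one line of protocol text. No participants are added beyond the 45 already planned, and no analysis changes.

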### Subjective Measures Taken During Study Sessions

1. Profile of Mood States – (POMS; McNair, Lorr, & Droppleman, 1971) The POMS consists of 72 adjectives commonly used to describe momentary mood states. The POMS is highly sensitive to the effects of drugs in similar samples of healthy volunteers (de Wit & Griffiths, 1991; Johanson & Uhlenhuth, 1980), and will be used to assess subjective tonic mood effects of the drug during the study sessions.
2. Drug Effects Questionnaire - (DEQ; Fischman & Foltin, 1991) The DEQ consists of questions on a visual analog scale about the subjective effects of drugs. Subjects are asked to rate the extent they feel a drug effect, whether they like or dislike the drug effect, and if given a choice would they want to take more of the drug. This is also be used to assess the pharmacodynamics of the drug effect during the study
3. Test of Self-Conscious Affect – (TOSCA; Tangney et al. 1989) The TOSCA is a 65-item questionnaire assessing responses to 15 scenarios involving social interaction. Subscales include shame, guilt, externalization, detachment, and alpha and beta pride.
4. Visual Analog Scales (VAS) – We plan to add single item visual analog scales tapping constructs that have previously been validated in our lab as uniquely sensitive to MDMA effects, including 'Insightful'; 'Sociable'; 'Confident'; 'Lonely'; 'Playful'; 'Dizzy'; "Loving"; "Friendly" and 'Restless'.
5. End of Session Questionnaire (ESQ) -- This is a short questionnaire addressing which drug the participants believed they received and how much they would like to take the drug again.

Cardiovascular measures – Blood pressure and heart rate will be periodically monitored using portable blood pressure cuffs. These measures will be used to both track the cardiovascular effects of the drug, and ensure participant safety.

Neuroendocrine measures – Saliva and plasma samples for oxytocin levels will be collected 120 minutes after drug administration. Saliva samples for cortisol analysis will be obtained using cotton wands (Salivette, Sarstedt, Germany). Levels of oxytocin in saliva and plasma will be measured using standardized methods at the University of Chicago Endocrinology Laboratory and University of Linkoping.

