fMRI studies indicate that individuals with autistic symptoms exhibit reduced responsiveness to affective touch in the orbitofrontal cortex (OFC) and superior temporal sulcus (STS), and individuals with diagnoses of ASD show reduced activity in these regions as well as in the bilateral insula and other regions involved in social and emotional processing (Voos et al. 2012, Kaiser et al. 2015). To understand the mechanism by which MDMA increases reactivity to affective touch, we will use functional magnetic resonance imaging to test the effects of the drug on BOLD responses to affective touch in individuals with a range of autistic traits. We hypothesize that individuals with high scores on the ASQ will exhibit reduced OFC, STS, and insular responses to affective touch, and that MDMA will enhance touch-related activity in these regions, correcting these deficits.

**Specific Aim 3: To determine the mediating role of oxytocin in the effects of MDMA on responses to affective touch in individuals with a range of autistic traits**

MDMA has been shown to increase plasma oxytocin, raising the possibility that oxytocin mediates the enhancement of social behavior induced by MDMA. Here we propose to assess whether the MDMA-induced rise in plasma oxytocin predicts enhanced responses to affective touch.

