
### **Procedure**

Orientation: Participants who meet criteria will first be scheduled for an orientation session. During this session, subjects will be informed that the capsules used in the study may contain a placebo, stimulant, a sedative/tranquilizer, or a cannabinoid/marijuana-like drug. This range of drug types is included to minimize expectancy effects. Participants will be given an oral description of the study procedures and the written consent form. After the experimenter reviews this information and the consent form with the subject, and answers any questions he/she may have, subjects will sign the informed consent document. Abstention from recent drug and alcohol use will be verified by breathalyzer and urine drug tests. Subjects will be asked about possible claustrophobia, and they will complete the scanning questionnaire to ensure that they have no metal implants.

Study Sessions: Two 4.5-hour sessions will be conducted, separated by at least 72 hours. Please see below for a full timeline of the study sessions. On study session days, participants will arrive at 9am, and complete a urine and breath screening for recent alcohol and drug use, and a pregnancy test (for women). Participants will then complete Time 1 measures of subjective mood and drug effects, and complete these same measures periodically throughout the study (see below). Participants will ingest the capsule at 9:30am. For the next hour, while the drug is absorbed, they will be allowed to relax and watch a movie or read a book, but will not be allowed to do work. Subjects will be escorted to the MRIRC at 10:30am to undergo an fMRI scan while performing the Touch Task. The scan will last approximately 45 minutes. Participants

will then be escorted back to the lab, where they will remain, completing subjective measures of the drug effect every hour until at least 1:30pm (when we expect drug effects will end), or until the effects of the drug return to baseline (as measured by both subjective report and cardiovascular variables).

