#### Timeline

9:00 am – Participant arrival, drug, alcohol and pregnancy testing, snack provided  
9:15 am – Time 1 Measures – POMS, DEQ, VAS, Blood Pressure, HR  
9:30 am – Administration of capsule  
10:00 am – Time 2 Measures - POMS, DEQ, VAS, Blood Pressure, HR  
10:30 am – Time 3 Measures - POMS, DEQ, VAS, Blood Pressure, HR  
11:00 am – fMRI scan with Touch Task  
11:45 am - end of scan  
12:30 pm – Time 4 Measures – POMS, DEQ, VAS, Blood Pressure, HR  
1:00 pm - Time 5 Measures – POMS, DEQ, VAS, Blood Pressure, HR  
1:30 pm - Participant leaves lab

End of study phone call: After the subject's last session we will conduct an end-of-study interview by phone. Participants will be asked to indicate how much they liked each study drug and how much they would want to take each drug again. Participants will also be asked to report which type or types of drugs they think they received at each session. Finally, participants will be told the study hypotheses, methods and the types of drugs that they received, and will be given a chance to ask any final questions.

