### **Neuroimaging:**

Imaging will be performed using a state-of-the-art Phillips Achieva Quasar Dual 16 Ch 3T MRI scanner. Three BOLD echo-planar imaging (EPI) scans will be acquired to measure responses to the tasks (gradient echo, 193 volumes; repetition time, 2,000 ms; echo time, 29 ms; flip angle, 76°; 35 interleaved 3mm-thick axial slices; matrix, 88×88; 2.5×2.5×3.0 mm^3 voxels; acceleration factor 2; and 3D prospective acquisition correction algorithm). Structural scans will also be acquired using a T1-weighted magnetization-prepared rapid gradient echo (MPRAGE) sequence for co-registration and normalization to the Montreal Neurological Institute (MNI) coordinate system. Head movement will be minimized through detailed instructions to participants and a conformal pillow which is fitted to the participant's head using a vacuum pump to withdraw air from the pillow. Participants are told to immediately alert the MRI technicians if they experience any discomfort or feel unwell, in which case the scan will be stopped and the participant removed from the scanner. The entire scan should require 45 minutes to complete.

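### The only oxytocin sample falls due at 11:30 am, inside the 11:00–11:45 scan slot and after touch has begun, so it cannot supply the temporal order that mediation in Aim 3 needs

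*Combined protocol and SAP*

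**What the plan says.** The neuroendocrine paragraph (under Subjective Measures Taken During Study Sessions) sets a single time for both matrices: "Saliva and plasma samples for oxytocin levels will be collected 120 minutes after drug administration". No pre-dose or pre-task oxytocin sample is described anywhere.

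The Timeline gives "9:30 am – Administration of capsule", then "11:00 am – fMRI scan with Touch Task", then "11:45 am - end of scan". It lists mood, drug-effect and cardiovascular measures at five times, but no saliva or blood collection.

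The Procedure section agrees on dosing ("Participants will ingest the capsule at 9:30am") but is looser on the scan: "Subjects will be escorted to the MRIRC at 10:30am to undergo an fMRI scan while performing the Touch Task". It gives no scan start time and refers the reader to the Timeline for the full schedule. The Neuroimaging section gives the length: "The entire scan should require 45 minutes to complete".

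Specific Aim 3 is framed as the mediating role of oxytocin. Its working question is to "assess whether the MDMA-induced rise in plasma oxytocin predicts enhanced responses to affective touch". According to the Affective Touch Task section, those responses are rated in the scanner.

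**The concern.** Two things follow from these passages.

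The first is practical. The sample falls due while the Timeline has the participant in the scanner, and the plan does not say what staff should do. They can break into the touch fMRI, which is the outcome of Aim 2 and also carries the pleasantness ratings of Aim 1. Or they can sample later than specified, with no stated time.

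The second is inferential. A mediator should be measured before the outcome it is meant to transmit an effect to. Here the only sample comes after touch stimulation has started, so the measured level reflects the drug plus whatever touch itself does to oxytocin. Subtracting placebo does not remove that component: touch is given in both sessions, and the hypothesis is that MDMA changes the response to it. An association between the oxytocin difference and the touch difference could then run in either direction.

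**Working it through.** **Inputs.** Capsule 9:30 am (Procedure, Timeline); sample at +120 min (neuroendocrine paragraph); scan 11:00 to 11:45 (Timeline); scan length 45 min and three functional runs of 193 volumes at 2 s (Neuroimaging); escort at 10:30 (Procedure); 45 participants, two sessions.

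**1. Reproduce the plan's own figure.** 11:00 + 45 min = 11:45, matching the stated end of scan.

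**2. Sample time.** 9:30 + 120 min = 11:30.

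**3. Position within the scan slot.** The scan runs from 11:00 − 9:30 = +90 min to 11:45 − 9:30 = +135 min. The sample is due 11:30 − 11:00 = 30 min after scan start and 11:45 − 11:30 = 15 min before scan end. If the scan is not interrupted, the earliest possible sample is at +135 min, before any escort time.

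**4. Latest possible start of touch.** Functional acquisition is 3 × 193 × 2 s = 1,158 s = 19.3 min. If these runs carry the touch task and are placed last, touch starts no later than 45 − 19.3 = 25.7 min (25 min 42 s) after scan start.

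**5. Compare the possible schedules.** The first two rows use scan starts that the Procedure text could allow; the third is the Timeline.

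| Scan start | Scan end | Latest touch start | Sample at 11:30 |
|---|---|---|---|
| 10:30 | 11:15 | 10:55:42 | feasible, after the scan |
| 10:45 | 11:30 | 11:10:42 | only just feasible, at scan end |
| 11:00 | 11:45 | 11:25:42 | inside the scan |

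For the scan to be over by 11:30 it must start by 11:30 − 45 min = 10:45. In every row touch has begun before 11:30.

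**6. Extent.** The planned number of session samples is 45 × 2 = 90. With uninterrupted scans, all 90 follow touch exposure.

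**Assumption in step 4.** Touch is the only task in the Timeline, so all three runs are assigned to it. Data Analysis also mentions a social interaction task that the Timeline does not schedule. If touch used only the last two runs (2 × 193 × 2 s = 772 s = 12 min 52 s), it could start at 11:45:00 − 12:52 = 11:32:08, and a sample that interrupted the scan at 11:30 would precede it. The plan describes no such arrangement, and it would still require stopping the scan.

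**The case against.** The best case on the other side has four parts.

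- **Feasibility.** A reader might infer that the sample simply cannot be taken on time. The documents do not support that without qualification: under the Procedure text a scan starting by 10:45 leaves 11:30 free. What stands against this is that the Procedure defers to the Timeline, and the Timeline also has Time 3 measures at 10:30. The supportable statement is that the three sections must be reconciled. Nor do the documents show that the task is under way at 11:30: 19.3 minutes of functional runs need not fill 45 minutes, so touch may already be finished.
- **Estimability.** A reader might infer that Aim 3 cannot be answered at all. That goes too far. The MDMA-placebo oxytocin difference at a common time, its relation to the touch ratings, and the planned group ANOVA on oxytocin can all still be computed. What is lost is temporal order.
- **Size of the reverse path.** The documents give no figure for any effect of brushing on oxytocin, whereas the Background states that MDMA itself raises plasma oxytocin. The reverse path may be small. The design cannot show that it is, but no magnitude can be claimed.
- **Slippage.** It is tempting to add that late samples would differ between sessions and add noise. The plan does not say so. If both samples were taken at scan end, the delay would be about equal in the two sessions.

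It is also fair to say that moving the sample would not by itself deliver mediation, since Data Analysis specifies only ANOVAs for oxytocin. A pre-touch sample is necessary for the claim, not sufficient.

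**Conclusion.** The concern holds in a limited form. On the Timeline, the only oxytocin sample is due 30 minutes into a 45-minute scan. It must either interrupt the scan or move to +135 minutes or later. The Procedure text avoids the clash only with a scan start by 10:45. On both schedules the sample comes after touch has begun, given that the functional runs carry the touch task. Aim 3 can therefore yield an association between the oxytocin difference and the touch response, but not the order its mediation claim needs. Any effect of touch on oxytocin, of unknown size, is included in the measured level.

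The clash of times is certain from the documents. That no sample can be taken during scanning rests on no such procedure being described. Aims 1 and 2 do not depend on oxytocin and are affected only if a scan is interrupted to obtain the sample.

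**What to change.** 1. Reconcile the scan start in Procedure and Timeline with the sampling time in the neuroendocrine paragraph.
2. Add an oxytocin sample to the Timeline before scanner entry, at the same post-dose time in both sessions. Name it as the Aim 3 predictor and record actual clock times. The investigators should choose the time, because the documents give no time to peak for oxytocin.
3. State in Data Analysis how this sample will be related to the touch response, since the present ANOVAs do not address prediction or mediation.
4. If only a sample after the scan is kept, fix its time outside the scan slot, label it post-touch, and restate Aim 3 as an association.

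**Cost.** This is a change of wording and one Timeline entry. Moving the sample leaves the number at 90; keeping a second, post-scan sample as well would make 180. An earlier sample may show a smaller drug effect on oxytocin. A blood draw shortly before the task could affect mood or ratings, though it would be made in both sessions alike. These costs should be weighed before data collection, because a missing pre-touch sample cannot be recovered afterwards.
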